5.7 Withdrawal of Subjects

 Describe any anticipated circumstances under which subjects will be withdrawn from the research without their consent.

A subject may be withdrawn if the event of severe increase of PTSD symptoms, disruptive behavior (e.g., yelling during sessions, conflict with another subject), non-compliance (e.g., never attends training sessions), changes in medical condition (e.g., severe illness precluding participation), changes in psychotropic medications, and unforeseeable circumstances (e.g., death in family; offer of full-time employment).

 Describe the consequences of a subject's decision to withdraw from the research and the procedures for orderly termination of participation by the subject (e.g., the subject contacting the investigator for an end-of-study visit).

Participants are told they can withdraw at any time. Should the investigator decide to terminate a subject's participation, she will contact the participant to discuss the reasons for termination. The investigator will also make a follow-up appointment if requested by the participant to discuss further any concerns expressed by a participant.

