### **Progress to date**

- Study was conducted at both SFVAMC and VA NCHCS in Martinez sites.
- Staff was hired and trained in study recruitment, assessment and cognitive training procedures.
- Study actively recruited subjects at both sites:
  - 545 letters describing the study have been mailed to potential participants; 218 detailed telephone screens have been conducted; 76 participants have been enrolled.
- To help enhance recruitment, researchers has made extensive efforts to enroll Veterans, including providing IRB-approved recruitment material to VA Outpatient clinics, Veteran Centers, State of California Department of Rehabilitation Veteran services programs, State of California Employment Development Department disabled Veterans outreach, State of California County Veterans services, community college Veteran affairs offices.
- Presentations describing the aims of this study have been made by PI and co-investigators to clinicians and researchers at both SFVAMC and VA NCHCS in Martinez, and at the: VINS21 TBI Polytrauma meeting 2014, 2015, 2016; and 2018; American College of Rehabilitation Medicine Conference October 2015; VA Psychology Leadership Conference May 2015 and May 2017; 10 World Congress on Brain Injury in April 2017; International Neuropsychological Society Meeting February 2016 ,February 2017, February 2018 and February 2019; 8th Federal Interagency Conference June 2018, and American Psychological Association Conference August 2018.
- Study is closed for enrollment, last follow-up on 12/30/18. Data analysis has started.
- Preliminary results from 40 participants who completed the training indicate that at week 5, after GOALS training, but not after EDU training, participants significantly improved on neuropsychological measures of attention/executive function, complex functional task performance and measures of emotional regulation. Participants reported incorporating trained strategies into their daily lives.

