5.6 Data Analysis

• Provide sample size determination and analysis (include anticipated rate of screen failures, study discontinuations, lost to follow-up etc.).

We estimated sample size requirements for the primary hypotheses for each aim based on the actual preliminary data from veterans who underwent GOALS training. For Attention and Executive Function Overall Domain z score (AVEXE) we found a standardized effect size of 1.2, for the GPS Overall Domain Score (GPSTA) and the Mayo Portland Adaptability Inventory Total Score (MPTST) we found a standardized effect size of 1.1, and for the POMS Total Mood Disturbance Score (POMSTMDZ) we found a standardized effect size of 0.8. Therefore, using the lowest effect size we would estimate that a feasible sample size of 42 patients (21 per group) for each intervention (GOALS and EDU) should yield a power of .80 at an alpha level of 0.05 to detect a standardized effect size of 0.8 or larger.

• Describe how, where and by whom the data will be analyzed.

Tests of repeated measures will be used to assess the effects of the training interventions on pre- and post- intervention measurements. Intervention group x time interactions will be assessed using ANOVA and specific relationships will be tested using paired T-tests.

Practice Effects: Because of repeated testing, improvements on some assessments may be partially due to practice. As a sensitivity analysis, we will compare tests using absolute change scores (as described above) to those using a change index that corrects for practice effects [70]. Specifically, change is operationalized as ((X2-X1)-(M2-M1))/SED, where X1, M1, and X2, M2 are the baseline and follow-up scores for a participant and corresponding group means, respectively; SED is the standard error of the difference. These results will be compared to those obtained from the regression models.

The PI and co-investigators will perform data analysis.

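### Withdrawal may be related to outcome, while the named tests in their usual form use only people with every compared visit; the 6-month within-person claims can be biased, in an unknown direction

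*Combined protocol and SAP*

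**What the plan says.** Section 5.7 of the combined protocol and SAP answers a prompt about removing people without their consent. Its list begins "A subject may be withdrawn if the event of severe increase of PTSD symptoms, disruptive behavior" and ends with "changes in psychotropic medications, and unforeseeable circumstances (e.g., death in family; offer of full-time employment". On termination it describes a conversation and, if requested, an appointment to discuss concerns. It mentions no further outcome assessment.

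Section 5.6 states: "Tests of repeated measures will be used to assess the effects of the training interventions on pre- and post- intervention measurements". It continues: "Intervention group x time interactions will be assessed using ANOVA and specific relationships will be tested using paired T-tests". A practice-corrected change index is the only sensitivity analysis, and of it the section says: "These results will be compared to those obtained from the regression models". Those models are described nowhere else. No analysis set or missing-data method is given, although the section's own prompt asks about discontinuations and loss to follow-up.

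Section 5.2 expects 42 of 54 to complete, after about 80 are recruited and enrolled. EDU-first participants start GOALS after week 5 (section 5.1).

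The 6-month reference differs by place. The Protocol's research questions use baseline for Question 1 and pre-GOALS performance for Questions 2 and 3. The abstract of the combined document uses baseline for all three domains.

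The Protocol's progress report says "76 participants have been enrolled" and gives one result: "Preliminary results from 40 participants who completed the training indicate that at week 5". It adds: "Study is closed for enrollment, last follow-up on 12/30/18. Data analysis has started".

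**The concern.** Several withdrawal grounds lie close to the outcomes themselves. Worsening PTSD bears on the emotional-regulation measures, and a job offer bears on daily functioning. If the people removed would have changed differently from those who stay, a test on those who stay estimates the wrong mean change.

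The 6-month claims are the most exposed. By then both arms have had GOALS, so the claim rests on change within person, and loss that is identical in the two arms does not cancel.

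GOALS versus EDU is better protected, but not fully. It is unbiased only if loss has both the same rate and the same relation to outcome in each arm. If the group-by-time ANOVA covers all visits, people lost after week 5 also drop out of the week-5 comparison.

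**Working it through.** **Inputs from the documents.** 54 enrolled and 42 completing (section 5.2); 21 per group and planned effects of 0.8 to 1.2 (section 5.6). Loss is p = 12/54 = 0.222, and 42/(1 − 0.222) = 54 returns the enrolment target. The documents give no figure for missing-data bias and no counts by reason, arm or visit.

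**Assumption.** Net correlation c between removal and change is 0.1, 0.3 or 0.5. Reasons that pull in opposite directions lower c.

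**1. Shift in mean change among those remaining.** Remove the lowest fraction p of a latent normal score that correlates c with change. The shift is c × φ(z_p)/(1 − p) = c × 0.2978/0.7778 = 0.383c.
- c = 0.1, 0.3, 0.5 gives 0.038, 0.115, 0.191 SD of change.
- The sign reverses if the highest scorers are removed.
- 10% loss gives 0.02 to 0.10; 30% loss gives 0.05 to 0.25.

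**2. Effect on a 6-month paired t-test.** With n = 42 the SE is 1/√42 = 0.154 SD. If the true change is 0 and those lost were doing worse, the chance of a significant gain (noncentral t, 41 df) is 4.3%, 10.9% or 22.7%, against 2.5%.

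**3. Size against the plan.** 0.038/0.8 = 5% and 0.191/0.8 = 24% of the smallest planned effect. The SD units may differ.

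**4. GOALS versus EDU.** The SE is √(2/21) = 0.309 SD.
- Outcome-related loss before week 5 in one arm only: bias 0.04 to 0.19 SD.
- Equal rates but opposite reasons by arm: twice that, 2 × 0.038 to 2 × 0.191 = 0.08 to 0.38 SD. The top of this range exceeds the SE.

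**5. What a mixed model can and cannot repair.** Simulation: four visits, equal between-visit correlation 0.5 / 0.7, true change 0, c = 0.5, 22% loss of those doing worse, one million people, baseline-SD units.

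| Loss | Contrast | Complete-case error | Mixed-model error |
|---|---|---|---|
| A. After week 5, driven by observed week-5 change | 6 months − baseline | +0.10 / +0.07 | 0 |
| A | 6 months − week 5 | −0.10 / −0.08 | 0 |
| A | 6 months − pre-GOALS, equal arms pooled (baseline if GOALS-first, week 5 if EDU-first) | about 0 | 0 |
| A | Week 5 − baseline, four-visit completers | +0.19 / +0.15 | 0 |
| A | Week 5 − baseline, everyone with both visits | 0 | 0 |
| B. After week 5, driven by unseen 6-month change from baseline | 6 months − baseline | 0.19 / 0.15 | 0.13 / 0.11 |
| B | 6 months − week 5 | about 0.10 / 0.08 | 0.13 / 0.11 |
| C. Before week 5, driven by unseen week-5 change | Week 5 − baseline | 0.19 / 0.15 | 0.15 / 0.13 |

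The mixed model removes error that observed scores explain (A). It removes only about 14% to 23% in C, and in B it does worse than complete cases on the week-5 reference.

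**6. Reach of a shift analysis.** The mean gap between people remaining and removed is c × φ(z_p) × [1/(1 − p) + 1/p]. At 22% loss this is 1.72c, or 0.86 SD at c = 0.5. At 10% loss it is 0.97 SD. A range of ±0.5 SD covers c only up to about 0.29 at 22% loss; ±1.0 SD covers both cases.

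**The case against.** **The undefined regression models may already use all available data.** This is possible. Two regression textbooks whose titles include repeated-measures models stand in the reference list just before the source cited for the change index. Section 5.6 cites neither and describes no such model. A reader might infer that the plan excludes people with incomplete data; the text does not establish that, only that the named tests do so in their usual form.

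**Such withdrawals may be rare.** Section 5.1 makes termination one of several possible responses to worsening PTSD, and section 5.4 asks that therapy stay the same for six months. Both may reduce the number, and the 12 expected losses cover all reasons. This stands, and is why no size can be fixed.

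**The effect is too small to matter.** If the true effects are near those planned, a shift of 0.04 to 0.19 SD is unlikely to reverse the conclusion. This largely stands. The false-gain figures apply only when the true change is near zero and those lost were doing worse.

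**Stronger readings the documents do not support.**
- That results are inflated: losing people who worsen raises the estimated gain, but losing people who improve lowers it.
- That 36 of 76 dropped out: the progress report does not say why the preliminary result covers 40.
- That the same withdrawals push the Question 2 and 3 claims one way and Question 1 the other: with the pooled pre-GOALS reference, the complete-case error in scenario A is about zero.

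**Conclusion.** The concern holds in a limited form. Withdrawal grounds that may relate to outcome, tests that usually need every compared visit, and no stated analysis set or missing-data method leave the 6-month within-person claims open to bias, even with identical loss in both arms. Direction and actual size are unknown. At 22% loss and an assumed c of 0.1 to 0.5, the shift is 0.04 to 0.19 SD of change.

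The week-5 contrast is unbiased only under the same rate and the same relation to outcome in both arms. Loss after week 5 leaves it untouched only in a two-visit analysis. With opposing reasons by arm the bias could reach 0.08 to 0.38 SD.

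A reader might infer that a mixed model alone settles the matter. It does not when loss depends on change that no visit recorded. Confidence is medium, because c has no basis in the documents and the undefined regression models might soften the point.

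**What to change.** Write a dated addendum, disclosed as written after the preliminary results from 40 participants:

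1. Keep the planned tests, labelled complete-case, with the number analysed at each visit. Run GOALS versus EDU on baseline and week 5 only, so that later loss removes nobody.
2. Alongside them, report a likelihood-based mixed model (arm, visit, arm × visit) on all randomised participants as assigned, using every assessment collected, including those from people later withdrawn. Say what the regression models in section 5.6 are. State that the mixed model corrects for loss explained by observed scores, and may not help, or may do worse on some contrasts, when loss depends on unseen change.
3. Reconcile the 6-month reference between the Protocol's research questions and the combined document's abstract. State the reference and how arms are combined; report both references if this stays unresolved.
4. Add a missing-not-at-random analysis that shifts unobserved outcomes in both directions, in both arms and in one arm only. Express shifts in SD of change, go out to at least ±1.0 SD, and report where the conclusion changes.
5. Tabulate withdrawals by arm, reason and last visit.

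The cost is analysis time. Last follow-up has passed, so no visits or participants are added. The additions carry a post hoc label, and the estimated effect may come out smaller. No clinical ground for withdrawal is altered.

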6.0 Reporting

 Include procedures for reporting unanticipated problems, serious adverse events, and protocol deviations.

All research staff has been directed to document unanticipated problems or adverse events and to notify the Principal Investigator of any unanticipated problem or adverse event. Investigators will follow up with subjects (in person or by telephone call) until the resolution of the adverse event and will ensure that appropriate medical care is provided. Researchers will complete SAE

or UAP reports. Reports will be submitted to the VA Central IRB within 5 business days after the reporting individual becomes aware of the occurrence.

7.0 Privacy and Confidentiality

• Describe whether the study will use or disclose subjects' Protected Health Information (PHI).

Screening subjects will include review of VA medical records.

 Describe the steps that will be taken to secure the data (e.g., training, authorization of access, password protection, encryption, physical controls, Certificates of Confidentiality, and separation of identifiers and data)

Electronic data will be stored on VA computer hard drives and server, all encrypted per VA guidelines. Paper records will be kept in locked cabinets in locked VA offices.

If VA desktop computers are unavailable (e.g., being used by other researchers), research staff may use VA laptops to enter/save research data (e.g., de-identified test scores) and then transfer data to r drive directly from laptop or, if applicable, transfer to VA desktop computer via USB drive. Researchers will also use laptops for email and files that don't involve subject data (e.g., research design, materials for presentations or publications, if desktop computers unavailable or if out of the office).

The USB drives have security features (activated by thumb swipe or password) that prevent them from being used by anyone other than the researcher to whom they are assigned. Researchers may use the USB drives to transfer information from a VA laptop to a VA desktop computer for further data entry/calculations when the desktop computer becomes available. The data would be uploaded to the VA server when data entry/calculation is complete.

8.0 Communication Plan

- Include plan for ensuring all required local site approvals are obtained and notifying the Director of any facility where the research in being conducted but the facility is not engaged.
 - N/A both sites are engaged
- Include plan for keeping all engaged sites informed of changes to the protocol, informed consent, and HIPAA authorization
 - The staff will be the same at both sites.
- Include plan for informing local sites of any Serious Adverse Events,
 Unanticipated Problems, or interim results that may impact conduct of the study.

- Notify by telephone and email local facility's institutional official and R & D
 Committee of any SAE, UAP and interim results that may impact conduct of the study
- Complete and submit SAE/UAP documentation as required by the local facility and local facility's R&D Committee. These documents will be uploaded to the Central IRB website
- Include plan for ensuring the study is conducted according to the IRB-approved protocol.
 - Prior to implementation of study, thoroughly train all research team members in study and IRB procedures and documents
 - Create and distribute written study procedure protocols kept in paper and electronic copy formats
 - Distribute IRB materials on procedures and report forms and maintain current IRB materials in paper and electronic copy formats
 - Hold weekly conference calls to address questions and resolve issues regarding study conduct, protection of human subjects, and IRB guidelines and forms.
 - Encourage open communication between research team members and PI/SC to address questions or concerns about study procedures and protection of human subjects. Open communication will be encouraged by holding weekly meetings and/or conference calls in which the PI specifically asks members of the team to voice questions and concerns about any aspect of the study. The PI will also encourage the research staff to email or call about issues or concerns if they prefer to use those channels.
- Include plan for notifying all local facility directors and LSIs when a multi-site study reaches the point that it no longer requires engagement of the local facility (e.g., all subsequent follow-up of subjects will be performed by the PI from another facility).
 - The PI/SC will notify the Local Facility Director in writing (paper and email) when the study no longer requires engagement of the local facility

